5.3. Study periods

Follow-up visit is scheduled at 90 (+/-7) days. The maximal observational period for a randomized patient would be 90 (+/-7) days. The study end date will be at 90 days after the last patient. At this time, it is expected that the majority of patients will have complete follow-up at 90 days. All patients must be followed for 90 days or until death prior to completion of study period.

6. STUDY POPULATION

Adult patients with STEMI diagnosed through the VHR Program will be reviewed for treatment. For patients presenting direct to the cardiac catheterization laboratory patients will be assessed by the study team prior to treatment. Fifteen (15) patients will be enrolled once inclusion / exclusion criteria are fulfilled and informed consent is obtained.

6.1. Inclusion Criteria

Patients presenting with STEMI within 6 hours of symptom onset and:

- 1. Are expected to receive reperfusion therapy with primary PCI
- 2. Have a high-risk STEMI ECG defined as:
 - ≥2mm ST-segment elevation in 2 anterior or lateral leads; or

Sonothrombolysis in Patients with an ST-segment Elevation Myocardial Infarction Protocol#ST2017-Pro00067953

Version (3): 13-Feb-2017

- o ≥2 mm ST-segment elevation in 2 inferior leads coupled with ST-segment depression in 2 contiguous anterior leads for a total ST-segment deviation of >4mm
- 3. Age \geq 30 years.
- 4. Adequate apical and/or parasternal images by echocardiography

6.2. Exclusion Criteria

- 1. Isolated inferior STEMI without anterior ST-segment depression
- 2. Previous coronary bypass surgery
- 3. Cardiogenic shock
- 4. Known or suspected hypersensitivity to ultrasound contrast agent used for the study
- 5. Life expectancy of less than two months or terminally ill.
- 6. Known bleeding diathesis or contraindication to glycoprotein 2b/3a inhibitors, anticoagulants, or aspirin
- 7. Known large right to left intracardiac shunts.

7.0 STUDY OUTCOME EVENTS

7.1 Primary Outcome

Spontaneous reperfusion as assessed by pre PCI ECG complete ST-segment resolution (>50%) (immediately prior to angiogram) and pre PCI TIMI 2-3 flow on the diagnostic angiogram.

7.2 Secondary Outcomes

- 1. Complete ST-segment resolution (≥50%) at 30 minutes post PCI as assessed by the worst lead on electrocardiogram
- 2. Left ventricular function as assessed by left ventricular ejection fraction (LVEF) by echocardiography (ECHO) (Simpson method) assessed on day 1 (pre and post reperfusion), day 3±2 (discharge) and 90±2 days after infarction.
- 3. Left ventricular function as assessed by wall motion score index (WMSI) by ECHO assessed on day 1 (pre and post reperfusion), day 3±2 (discharge) and 90±2 days after infarction.
- 4. Left ventricular function as assessed by microvascular perfusion score index (MPSI) by ECHO assessed on day 1 (pre and post reperfusion), day 3±2 (discharge) and 90±2 days after infarction.
- 5. Left ventricular function as assessed by global longitudinal strain by ECHO assessed on day 1 (pre and post reperfusion), day 3±2 (discharge) and 90±2 days after infarction.

7.3 Safety Outcomes:

- 1. Allergic reaction to Definity®
- 2. Vasospasm in culprit coronary artery
- 3. Adverse events (see appendix)

8. DEFINITIONS OF STUDY OUTCOMES

8. 1 ST-segment Resolution

ECGs will be evaluated centrally at the ECG core laboratories (Canadian VIGOUR Centre, Edmonton, Canada) without knowledge of treatment, procedural results, or clinical outcomes. ST-E will be measured at the J point with magnified calipers to the nearest 0.05 mV. ST-E sums (ST-E) will be calculated as follows: for anterior infarction, the sum of ST-E in V1 to V6, I, and aVL; for inferior infarction, the sum of ST-E in leads II, III, aVF, V5, and V6. ST-segment depression will also be measured at the J point by similar methods. ST-segment deviation sums (ST-D) will be calculated by adding the sum of ST-segment depression measured in reciprocal leads to _ST-E. Leads II, III, and aVF will be considered potential reciprocal leads for inferior infarctions, and leads V1 through V4 will be considered potential reciprocal leads for inferior infarctions.

The resolution of ST-segment elevation (worst lead) prior to PCI and at 30 minutes post PCI will be classified according to the number of patients achieving complete ST-segment resolution (>50%) versus no ST-segment resolution (≤50%). The resolution of ST-segment elevation (worst lead) at discharge will be calculated using the discharge ECG using the above criteria.

8.2 Spontaneous Reperfusion

8.2.1 Angiographic spontaneous reperfusion

Angiographic spontaneous reperfusion is defined as TIMI flow grade 2-3 of the infarct related artery before PCI (first contrast injection) (37). Other definitions of spontaneous reperfusion (will be collected but not included as the primary endpoint)

8.2.2. Electrocardiographic (ECG) spontaneous reperfusion

ECG spontaneous reperfusion is defined as those patients who achieved complete (>50%) ST-segment resolution on the 12-lead ECG (worst lead) performed immediately prior to the coronary angiogram in patients undergoing primary PCI (37).

8.2.3 Echocardiographic spontaneous reperfusion

Echocardiographic spontaneous reperfusion is defined as score 1 or 2 in the infarct segments and/or recovery of systolic function during follow-up

9. STATISTICAL AND ANALYTICAL METHODS

The primary efficacy analysis will include 15 patients in the study regardless of treatment they actually received in accordance to the intention-to-treat (ITT) principle. A per protocol analysis will be performed on those patients who actually received sonothrombolysis. For the primary outcome, 12-lead electrocardiograms will be collected prior to PPCI and epicardial patency will be assessed at the time of the diagnostic angiogram. For the secondary endpoints, myocardial perfusion will be assessed based on the 12-lead ECG 30 minutes post PCI for complete ST-segment resolution. Myocardial contrast echocardiography will be performed using a commercially available echocardiography scanner (Epiq, Philips) with a diagnostic ultrasound transducer (X5-1) and a preset for myocardial perfusion imaging. 4-, 2- und 3-chamber views.

10. TRIAL ORGANIZATION

This study will be conducted in Edmonton through the Vital Heart Response Program and the Alberta Cardiovascular and Stroke center (ABACUS). The principle investigator, co-investigators and research coordinator will meet regularly (monthly) and will address the day-to-day operations of the trial.

11. DATA MANAGEMENT

Data will be managed at Alberta Cardiovascular and Stroke center (ABACUS) located at the University of Alberta Hospital Edmonton, Canada.

11.1. Case Report Forms

Case report forms (CRF) will be designed and managed by the principle investigators involved in the research study. Key demographic and procedural data along with outcome and adverse events will be collected. The CRF must be signed by the investigator or designate at study completion. Signing of the 'Study completion – Investigator's statement CRF' is considered to be the final authorization of the CRFs.

11.2. Data Quality Control

All data will be reviewed to ensure completeness and accuracy of information (CRF). Any concerns will be immediately addressed with modifications made accordingly.

12. FEASIBILITY AND LIMITATIONS

Considering the patients admitted with STEMI during the last year, recruitment of 15 participants within 1 year appears to be feasible. An Epiq/Philips ultrasound scanner will be available for almost 24/7 in ABACUS and can be moved within minutes into ER or the cath laboratory. However, a sonographer or fellow to perform the ultrasound imaging may not always

Sonothrombolysis in Patients with an ST-segment Elevation Myocardial Infarction Protocol#ST2017-Pro00067953 Version (3): 13-Feb-2017 be available when a suitable patient with STEMI arrives. In order to avoid delays in the standard treatment of the myocardial infarct, the sonographer or fellow on call will receive a telephone call from the attendings in the cath lab immediately after they were notified by the ambulance that a patient with STEMI is approaching. That will give the echo fellow or sonographer enough time to be ready for ultrasound imaging with contrast, when the patient arrives. If the echo personnel arrive too late, no sonothrombolysis will be performed.

The current protocol mandates contemporary treatment for patients with STEMI undergoing reperfusion therapy. We do advocate therapy according to the current consensus guidelines to promote universal care (38, 39).

13. ETHICAL AND REGULATORY STANDARDS

13.1. Good Clinical Practice

The study will be conducted in accordance with both the Tri-Council Policy Statement (40) and Good Clinical Practice Guidelines (41).

13.2. Informed Consent of the Patient

Patients who meet all inclusion criteria and none of the exclusion criteria are deemed eligible. Before being enrolled into the clinical study, the patient must provide written consent to participate in the study after the nature, scope and possible consequences of the clinical study have been explained both orally and in writing.

13.3. Approval of the Study Protocol

Before the start of the study, the study protocol and the informed consent form used at the site and other appropriate documents must be submitted to and approved by the local Ethics Committee or Institutional Review Board (REB) and the appropriate regulatory authorities in accordance with local legal requirements.

13.4. Maintenance of Records

The Investigator agrees to obtain a correctly completed informed consent form for each patient included in the study. The investigator will maintain a personal list of patient numbers and patient names to enable records to be found at a later date.

The Investigator must maintain all study records, patient files and other source data for the maximum period of time permitted by the hospital, institution or private practice. However national regulations should be taken into account, the longest time having to be considered.

14. STUDY MONITORING

Sonothrombolysis in Patients with an ST-segment Elevation Myocardial Infarction Protocol #ST2017-Pro00067953 Version (3): 13-Feb-2017 14.1. Responsibilities of the investigator(s)

The Investigator(s) undertake(s) to perform the study in accordance with Good Clinical Practice (41).

The Investigator is required to ensure compliance with respect to the invasive strategy schedule, visit schedule and procedures required by the protocol. The Investigator agrees to provide all information requested in the CRF in an accurate and legible manner according to instructions provided.

14.2. The use and completion of case report forms (CRFs)

It is the responsibility of the Investigator to prepare and maintain adequate and accurate CRFs. All CRFs should be completed in their entirety in a neat, legible manner to ensure accurate interpretation of data.

15. ADMINISTRATIVE RULES

15.1. Curriculum vitae

An updated copy of the curriculum vitae for each Investigator and co-Investigator will be provided to the principle investigator prior to the beginning of the study.

15.3. Record retention in investigating center(s)

The Investigator must maintain all study records, patient files and other source data for the maximum period of time permitted by the institution.

16. OWNERSHIP OF DATA AND USE OF THE STUDY RESULTS

The investigators of the study have ownership of all data and results collected during this study. Full publication rights of the study data solely reside with the investigators.

17. PUBLICATIONS

All study presentations and/or publication of the results will be based on clean, checked and validated data in order to ensure the accuracy of the results. All analyses for publication will be provided by ABACUS. The responsibility for presentations and/or publications belongs to the investigators. The final content of the manuscript is the responsibility of the investigators. Publication of the main findings of this study will be authored based on the contributions of the individuals to the overall study.

18. POTENTIAL IMPACT OF STUDY

Once completed, this will provide prospective data on the efficacy and safety of sonothrombolysis which we believe will lead to a randomized clinical trial of contemporary PCI STEMI patients (treated with PPCI or fibrinolysis) aimed at assessing the efficacy of sonothrombolysis as an adjuvant therapy to improve microvascular function.

APPENDIX

Adverse Events

An Adverse Event (AE) is defined as any untoward medical occurrence, including an exacerbation of a pre-existing condition, in a patient in a clinical investigation who received a pharmaceutical product. The event does not necessarily have to have a causal relationship with this treatment.

A Serious Adverse Event (SAE) is defined as any AE which results in death, is immediately life-threatening, results in persistent or significant disability / incapacity, requires or prolongs patient hospitalisation, is a congenital anomaly / birth defect, or is to be deemed serious for any other reason representing a significant hazard, which is comparable to the aforementioned criteria.

Adverse events occurring during the course of the clinical trial (i.e. from signing the informed consent) will be collected, documented and reported by the investigator.

Reporting of Serious Adverse Events (SAE)s:

• On an SAE form:

For the following events an SAE form (in addition to entering the SAE data in the CRF) will need to be completed and mailed for expedited reporting:

- o Serious and treatment-related SAEs
- Serious, not treatment-related and not mentioned on the 'list of STEMI-related events'

For each SAE, the investigator will provide the onset, end, treatment required, outcome, seriousness and action taken with the investigational drug. The investigator will also determine the relationship of the investigational drug to all SAEs.

The basis for judging the causal relationship between the investigational product and the SAE is described below.

Causal Relationship*		
Yes	There is a reasonable causal relationship between the study drug administered and the AE.	
No	There is no reasonable causal relationship between the study drug administered and the AE.	

^{*}Medical judgement should be used to determine the relationship, considering all relevant factors, including pattern of reaction, temporal relationship, de-challenge or re-challenge,

Sonothrombolysis in Patients with an ST-segment Elevation Myocardial Infarction Protocol#ST2017-Pro00067953

Version (3): 13-Feb-2017

confounding factors such as concomitant medication, concomitant diseases and relevant history.

These completed SAE forms need to be mailed within 24 hours (1 workday) to the coinvestigators after the Investigator (or any member of the study team) has become aware of the event. Timelines are the same for initial reports and for follow-up reports. The investigator and the coinvestigators will assess the treatment relationship, the category classification, listedness and seriousness of reported SAE cases. Expedited reporting of serious adverse events, e.g. suspected unexpected serious adverse reactions (SUSARs), will be done according to local regulatory requirements within the required timelines.

• In the eCRF:

Any SAE, whether or not considered related to the study medication, and whether or not the study medication has been administered, must be reported immediately in the eCRF.

Reporting of Non-Serious Adverse Events:

Non-serious events need to be recorded in the CRF

THE FOLLOWING ADVERSE EVENTS ARE EXPECTED AS DISEASE-RELATED **EVENTS (I.E. RELATED TO ACUTE MYOCARDIAL INFARCTION):**

Arrhythmias

All arrhythmias occurring later than 3 hours after fibrinolysis All arrhythmias in patients who did not receive fibrinolysis

Ischaemia and symptoms of coronary artery disease

Angina pectoris (stable)

Angina pectoris (unstable)

Back pain (of cardiac origin)

Cardiac enzymes (abnormal)

Cardiac markers (abnormal)

Chest pain

Electrocardiogram abnormalities

Myocardial ischaemia

Myocardial reinfarction

Recurrent myocardial ischaemia

ST-elevation

Substernal chest pain

Substernal pain

Sonothrombolysis in Patients with an ST-segment Elevation Myocardial Infarction Protocol#ST2017-Pro00067953

Version (3): 13-Feb-2017

Artery disorders

Aortic dissection
Coronary artery dissection
Coronary artery disorder
Coronary artery thrombosis
Coronary occlusion
Vascular anomaly

Cardiac failure

Acute pulmonary oedema
Cardiogenic shock
Congestive heart failure
Cor pulmonale
Heart failure
Left heart failure
Pulmonary oedema
Haemodynamic and circulatory shock

Pericardium disorders

Pericardial effusion Pericarditis

Other cardiac disorders

Acute mitral regurgitation
Acute ventricular septum defect
Cardiac rupture
Cardiomyopathy
Electro-mechanical dissociation

Other events

Deep thrombophle bitis
Hypertension
Livedo reticularis
Peripheral oedema
Peripheral vascular disorder
Syncope

Sonothrombolysis in Patients with an ST-segment Elevation Myocardial Infarction Protocol#ST2017-Pro00067953 Version (3): 13-Feb-2017 Thrombocytosis Vascular disorder Venous thrombosis

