1.0 OVERVIEW OF STUDY DESIGN

Patients presenting with ST-segment elevation myocardial infarction undergoing reperfusion therapy (fibrinolysis or primary PCI)

All patients receive ASA and other standard therapies

IN-HOSPITAL AND 90-DAY FOLLOW-UP

Primary Outcome

1. Spontaneous reperfusion as assessed by a pre PCI ECG complete ST-segment resolution (>50%) (immediately prior to angiogram) and by pre PCI TIMI 2-3 flow on diagnostic angiogram..

Secondary Outcomes

- 1. Complete (>50%) ST-segment resolution at 30 minutes post PCI as assessed by the worst lead on electrocardiogram (ECG core lab).
- 2. Left ventricular ejection fraction (LVEF) by echocardiography (ECHO) (Simpson method) assessed on day 1 (pre and post reperfusion), day 3±2 (discharge) and 90±2 days after infarction.
- 3. Wall motion score index (WMSI) by ECHO assessed on day 1 (pre and post reperfusion), day 3±2 (discharge) and 90±2 days after infarction.
- 4. Microvascular perfusion score index (MPSI) by ECHO assessed on day 1 (pre and post reperfusion), day 3±2 (discharge) and 90±2 days after infarction.

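### In a primary-PCI-only trial every arrhythmia is on the disease-related list, and the causality scale names only the drug, so a serious arrhythmia attributed to the ultrasound can miss the expedited SAE form

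*Combined protocol and SAP*

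**What the plan says.** **When the form is due.** The Appendix (Reporting of Serious Adverse Events) gives two triggers: "Serious and treatment-related SAEs", and events that are "Serious, not treatment-related and not mentioned on the" list of STEMI-related events.

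**What is listed.** The list closing the Appendix contains, under Arrhythmias, "All arrhythmias in patients who did not receive fibrinolysis". Its companion line, for patients who did have fibrinolysis, lists only arrhythmias more than 3 hours afterwards.

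**Who is enrolled.** Section 6.1 requires that patients "Are expected to receive reperfusion therapy with primary PCI". Section 1.0 still speaks of "reperfusion therapy (fibrinolysis or primary PCI"), which does not match the eligibility criteria or the Synopsis.

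**How causality is judged.** The Appendix asks for the relationship of the investigational drug to all SAEs on a Yes/No scale. The No level reads "There is no reasonable causal relationship between the study drug administered and the AE". The adverse event definition is likewise tied to receipt of a pharmaceutical.

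**What the treatment is.** The Synopsis (Treatment) describes intermittent high-MI imaging during a Definity infusion. Section 5.2 makes the high-MI impulses the therapeutic step, and Table 1 places sonothrombolysis both before and after PPCI.

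**What follows a form.** Completed forms "need to be mailed within 24 hours (1 workday") to the co-investigators. They and the investigator then assess treatment relationship, listedness and seriousness of the reported cases. Separately, every SAE, related or not, must be entered in the eCRF immediately.

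**Vasospasm.** Section 7.3 makes culprit-artery vasospasm a safety outcome.

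**The concern.** The arrhythmia clauses suit a trial in which fibrinolysis is given. There, early arrhythmias after the lytic stay off the list and remain reportable. This trial has no corresponding window for sonothrombolysis, the treatment under study, so an arrhythmia during the impulses is classed with one arising days later.

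A listed event can then reach the form only through a finding of treatment-relatedness. The one scale provided for that finding asks about the drug and does not mention the ultrasound.

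What is at stake is prompt escalation. Section 2.0 names ventricular arrhythmia as a possible consequence of abrupt reperfusion, and Section 3.0 expects sonothrombolysis to enhance reperfusion before PCI, so an arrhythmia during treatment could be an effect of the intervention. With one arm and 15 patients there is no control group in which an excess could show. Case-by-case review of relatedness therefore carries much of the safety assessment.

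**Working it through.** The plan states no figure on this point, so the check is of the reporting rule as written.

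**Inputs**
- Rule (Appendix, two triggers): form required if serious AND (related OR not listed).
- Arrhythmia without fibrinolysis: listed, with no limit on time or severity (Appendix, list).
- Population: expected primary PCI (Section 6.1), hence no planned fibrinolysis.
- Causality, reading A: drug only (Appendix, scale and adverse event definition).
- Causality, reading B: whole treatment, ultrasound plus Definity (Appendix trigger wording, with the Synopsis definition of treatment).
- Assumption: the STEMI-related list in the trigger and the disease-related list at the end of the Appendix are the same list, although their titles differ.

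**Step 1. Which arrhythmias are listed?** With no planned fibrinolysis, the second clause applies to every arrhythmia, at any time. The rule then reduces to: form required if serious AND related.

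**Step 2. Apply the rule to a serious event attributed to the ultrasound impulses and not to the contrast agent.**

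| Event | Listed? | Reading A (related = No) | Reading B (related = Yes) |
|---|---|---|---|
| Arrhythmia | Yes | No form | Form |
| Culprit-artery spasm coded under a generic entry such as Coronary artery disorder | Yes | No form | Form |
| Culprit-artery spasm treated as not listed | No | Form | Form |

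**Step 3. Compare the rows.** For arrhythmia, the outcome turns wholly on which of two wordings in the same Appendix the investigator follows. For spasm, reading A fails only if someone codes a named safety outcome under a vague list entry. Spasm does not appear on the list by name.

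**Step 4. What is missed under reading A?** The form and the review that the Appendix attaches to reported SAE cases. The immediate eCRF entry is still required. The text does not say that an eCRF entry alone starts that review.

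**The case against.** The strongest reply is that the trigger says treatment-related, the Synopsis defines treatment as both components, and the Appendix asks for medical judgement on all relevant factors, including timing. An investigator could therefore judge an arrhythmia during the impulses related and send the form. The drug and the ultrasound are also hard to separate: Section 2.0 describes the mechanism as microbubble cavitation induced by the impulses, so even a drug-only scale need not give No. Both points stand. They make the literal reading one of two, and do not remove the conflict between the trigger and the only defined scale.

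A reader might infer that arrhythmias go unreported or unassessed. The documents do not support that. Causality is to be determined for all SAEs, listed or not; every SAE goes into the eCRF at once; and expedited reporting of SUSARs under local rules remains.

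A reader might also infer that vasospasm is exempt. It is a named safety outcome and not a named list entry, so as an unlisted serious event it needs the form whatever the causality.

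Nor should the vasoconstriction in three of six patients cited in Section 2.0 be read as a rate for this trial. That study used 20 µs pulses, and this protocol uses 5 µs in response.

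Finally, limiting expedited forms for expected disease events is a legitimate choice, and Section 2.0 gives some reason to expect arrhythmias with reperfusion. That supports having a list. It does not explain why the list is keyed to fibrinolysis and has no window around the study treatment.

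**Conclusion.** The point holds as a conflict within the Appendix that should be corrected. In the planned population all arrhythmias are listed, so a serious one needs the form only through treatment-relatedness. The defined scale, read literally, returns No for an event attributed to the ultrasound alone. Two investigators could route the same event differently.

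The gap is confined to the expedited form and the co-investigator review. It does not affect data capture, the primary outcome or its analysis. Vasospasm is a secondary part of the point and depends on generic coding.

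The conclusion assumes that the two list titles denote one list and that no enrolled patient receives fibrinolysis. No arrhythmia rate is given, so the expected number of misrouted events cannot be computed.

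**What to change.** 1. Word the adverse event definition, the causality instruction and the Yes/No scale as relationship to sonothrombolysis (contrast agent and/or ultrasound impulses), matching the Synopsis.
2. Replace the two fibrinolysis-based arrhythmia clauses, so that serious arrhythmias from the start of the contrast infusion to the end of the day-1 study procedures are not exempt from the SAE form. This window includes the post-PPCI sonothrombolysis in Table 1.
3. State that serious culprit-artery vasospasm is not covered by generic entries such as Coronary artery disorder or Vascular disorder.
4. Minor tidying: use one title for the list, and give a single deadline for the form, since 24 hours and one workday can differ.

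The cost is Appendix wording and a few extra SAE forms in 15 patients. Sample size, outcomes and analysis do not change.
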